Neuroinflammation in Obesity**Principal Investigator: [name]**

Washington University

[name]

[name]

[name]

[contact]

E-mail: [contact]

ClinicalTrials.gov NCT#: 04116229

Document date: August 25, 2020

Protocol

Version 6: August 25, 2020

SCHEMA

Title: Neuroinflammation in Obesity

Total N = 20 (10 non-obese and 10 obese), nondiabetic male and female adults

Screening

- Medical history
- Current psychiatric disorders as assessed by Structured Clinical Interview for DSM-IV¹
- Current binge eating disorder as assessed by Binge Eating Scale²

Inclusion criteria:

- Non-obese (BMI = 18 -25 kg/m²) or Obese (BMI ≥ 30 kg/m²)
- Age 18-75 years
- Any race or ethnicity
- Male or Female
- Native English Speaker

Exclusion criteria:

- Current or past diabetes
- Psychotropic medications
- Previous or current neurologic illness including but not limited to stroke, seizure, generalized dystonia, parkinsonism
- History of or current drug abuse
- Current mental illness
- Binge eating disorder
- Non-native speaker of English
- MRI contraindications
- Pregnancy (confirmed with negative urine pregnancy test unless postmenopausal or surgically sterilized)
- Currently lactating
- Tobacco use within the past month
- >350 lb

Protocol

Version 6: August 25, 2020

Title: Neuroinflammation in Obesity**TABLE OF CONTENTS**

Section		Page
	SCHEMA	2
1.0	BACKGROUND AND RATIONALE	4
2.0	OBJECTIVES	4
3.0	METHODS	4
	3.1. Research Subjects	4
	3.2. Experimental Design	5
	3.3. Statistical Analysis	7
4.0	DATA SAFETY MONITORING	7
	4.1. Human Subjects Education Certification	7
	4.2. Procedures for Maintaining Confidentiality and Data Security	8
	4.3. Risks and Benefit	8
5.0	REFERENCES	10

1.0 BACKGROUND AND RATIONALE

More than a third of individuals in the United States are obese³. Obesity has recently been associated with increased risk for cognitive impairment and dementia such as Alzheimer's disease (AD)⁴⁻¹⁰. In young and middle-aged people, higher BMI relates to diminished learning, memory, and executive function¹¹⁻¹⁴. Cournot et al. found that higher BMI during middle age is associated with impaired delayed recall at baseline and at several years follow-up¹¹. Long-term obesity (from age 25 through late midlife, mean age = 61 yrs) predicts lower Mini-Mental State Examination (MMSE) scores and impairments in memory and executive function in late midlife independent of age and education, according to the Whitehall II Cohort Study¹⁵. Although previous human studies have investigated structural and functional differences between obese and non-obese individuals, strong relationships between these differences and cognitive performance have not been found¹⁶. It is likely that a key specific component to obesity-related brain effects on cognition has yet to be studied.

Obesity is a disease characterized by chronic low-grade systemic inflammation¹⁷. We propose that **neuroinflammation** is a major mechanism by which young and mid-life overweight or obesity contributes to cognitive impairment. Reduced blood brain barrier integrity induced by chronic high fat diet is thought to be a major way in which pro-inflammatory elements cross over into the brain and induce neuroinflammation¹⁸. Indeed, recent studies in rodents show that diet-induced obesity induces neuroinflammation¹⁹⁻²³ accompanied by cognitive impairment^{19,23}. However, only a few studies have addressed these questions in obese humans^{22,24}.

The current proposal investigates whether indicators of neuroinflammation are present in **obese humans** and whether these indicators are associated with cognitive performance. We will use MR-based DBSI, an extension of diffusion weighted imaging (DWI) developed at Washington University School of Medicine (WUSM) by [name] that differentiates between axon/myelin integrity, axonal density, and extra-fiber components including inflammation and edema in white matter²⁵. In addition, we will use a complimentary MR-based multimodal approach that includes functional connectivity MRI (fcMRI) and quantitative gradient recalled echo (qGRE, GEPCI, SMART), which distinguishes neuronal, synaptic and glial components of the MR signal²⁶.

2.0 OBJECTIVES

The objective of this proposal is to use MRI imaging to identify indicators of neuroinflammation in obese individuals. Further, greater neuroinflammation should correlate with greater cognitive impairment in obese individuals.

Aim 1: To determine if obesity is associated with increased cellularity and glial levels in the brain using MR-based Diffusion Basis Spectrum Imaging (DBSI) and qGRE (GEPCI/SMART).
Aim 2: To determine if indicators of neuroinflammation, including cellularity and glial levels are associated with cognitive performance in obesity.

3.0 METHODS

3.1.1 Research Subjects:

We will study 10 non-obese and 10 obese adults, both male and female, who are non-diabetic, aged 18-75 years.

Protocol

Version 6: August 25, 2020

Inclusion criteria: Non-obese (18-25 kg/m²) or obese (BMI \geq 30 kg/m²), male or female, any race or ethnicity, aged 18-75 years.

Exclusion criteria: Exclusion criteria include the following: history of diabetes, >350 lb (scanner weight limit), binge eating disorder, history of or current serious neurological illness, current mental illness, not a native speaker of English, history of drug abuse or currently taking psychotropic medication, MRI contraindications. Additionally, participants will be excluded if they are currently pregnant (positive urine pregnancy test) or breastfeeding. Finally, any participant with tobacco use in the past month will also be excluded.

Sample size justification: We received funding to study 20 individuals. This is a pilot and feasibility study.

3.1.2. Recruitment:

We will call or email previous participants from a previous study of obesity (IRB#201104109; PI: [name]). Subjects will be screened on a private line in a private suite using the phone script. They will be informed of the nature of the experiment and, if interested, will be questioned about inclusion and exclusion criteria. Those subjects meeting these criteria, and expressing further interest after this screening will be scheduled for study visits.

We will also recruit through Volunteers for Health and make use of their services including Facebook, Centerwatch, and Twitter posts, and flyers (for email blasts and posting at various sites).

Upon arrival into the laboratory for the first session, if the investigators are satisfied that the subject meets all of the inclusion and exclusion criteria, and the subject agrees to participate, the Human Research Protection Office (HRPO) approved informed consent will be signed.

3.2. Experimental Design:

3.2.1. Facilities.

The MRIs will take place in a Siemens 3T scanner in the Center for Clinical Imaging Research (CCIR) at Barnes-Jewish Hospital or in the East Building at WUSM. Screening and cognitive testing will take place in a private testing room. Oral glucose tolerance tests (OGTTs) will take place at the Clinical Research Unit (CTRU) at WUSM.

3.2.2. Overview of Procedures.

Initially, potential subjects will be screened by a phone interview that assesses medical history. In addition, subjects will be screened for psychiatric disorders and Binge Eating Disorder using the SCID for DSM-IV¹. If they remain eligible for the study, they will be emailed a link to a REDCap survey on binge eating habits (<https://redcap.wustl.edu/redcap/surveys/?s=8WWXCWFLJR>; adapted from the Binge Eating Scale²). If their score is below the threshold for binge eating, they will remain eligible for the study. An informed consent document will be emailed to eligible volunteers. Obtaining informed consent will occur via email prior to the on-site study visit day. The OGTT, 90 min MRI scan and cognitive testing will occur during one on-site study visit day.

Protocol

Version 6: August 25, 2020

3.2.3. Imaging Methods:

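### Does the plan need to say how the OGTT and HbA1c results bear on the non-diabetic criterion?

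*Combined protocol and SAP*

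**What the plan says.** The target population is stated three times in the protocol. The schema lists "Current or past diabetes" among the exclusions. Section 3.1.1 describes adults "who are non-diabetic, aged 18-75 years", and a few lines later says "Exclusion criteria include the following: history of diabetes". No laboratory definition of diabetes is given.

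Section 3.2.2 says that "potential subjects will be screened by a phone interview that assesses medical history". Section 3.1.2 adds "Those subjects meeting these criteria, and expressing further interest after this screening will be scheduled for study visits", and has consent signed at the first session "if the investigators are satisfied that the subject meets all of the inclusion and exclusion criteria". Section 3.2.2 places consent differently: "Obtaining informed consent will occur via email prior to the on-site study visit day".

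The OGTT, MRI and cognitive tests share one on-site day (3.2.2). The stated use of the OGTT is to derive insulin secretion and sensitivity (3.2.4), the evident source of the insulin-resistance covariate for Aim 1 in section 3.3. HbA1c appears only in section 3.2.5, which gives a blood volume and names the tests, but no time point or use.

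Aim 1 is an ANCOVA of obese against non-obese. Aim 2 is a Pearson correlation in obesity with no covariates. The sample of 10 plus 10 is set by funding, and section 3.1.1 says "This is a pilot and feasibility study".

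**The concern.** Diabetes appears to be screened by history alone. The blood tests that could reveal undiagnosed diabetes are taken, at least for the OGTT, on the same day as the scan and cognitive tests. If a result then points to diabetes, section 3.3 does not say whether that person's data are kept, dropped or shown both ways, so the choice could be made after seeing the results.

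With ten per group, one person is 10% of a group. Aim 1 has some protection from the insulin-resistance covariate. Aim 2 has none, and one participant who is extreme on both the MRI metric and cognition could produce a correlation. A blood test with no stated purpose adds to the impression of an unfinished plan.

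**Working it through.** **1. The text.** The plan gives no figure on this point to reproduce, so the passages come first.

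- *Who belongs.* The schema excludes current as well as past diabetes, and section 3.1.1 defines the sample as non-diabetic. The later phrase in 3.1.1 mentions history only, but read with the other two it does not admit a person with current diabetes, however it is discovered.
- *When eligibility is settled.* It is tempting to say that every eligibility step precedes the OGTT. The text does not go that far. Section 3.2.1 places screening in an on-site testing room without giving its order in the day, the urine pregnancy test has no stated time, and HbA1c is itself undated. A screening use of HbA1c is therefore not ruled out.
- *HbA1c timing.* Section 3.2.2 describes one on-site day, and the other steps are by phone, email or electronic survey. A blood draw most naturally belongs to that day.

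**2. How likely is a case?** The prevalence p of undiagnosed diabetes is an assumption. The chance of at least one case among the ten obese participants is 1 − (1 − p)^10:

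- p = 2%: 1 − 0.98^10 = 18.3%
- p = 5%: 1 − 0.95^10 = 40.1%
- p = 10%: 1 − 0.90^10 = 65.1%

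**3. Effect on Aim 2.** Aim 2 is read as the obese ten, tested two-sided at 5% (the plan states no level), so the critical |r| is 0.632. Simulation: ten independent standard normal pairs, m cases moved by +d SD on the MRI metric and −d SD on cognition, 400,000 runs. The share with |r| > 0.632 was:

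| Shift d on both | m = 0 | m = 1 | m = 2 | m = 3 | m = 4 |
|---|---|---|---|---|---|
| 1 SD | 0.050 | 0.055 | 0.067 | 0.077 | 0.085 |
| 2 SD | 0.050 | 0.118 | 0.220 | 0.303 | 0.352 |
| 3 SD | 0.050 | 0.291 | 0.549 | 0.697 | 0.767 |

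Weighting by the Binomial(10, p) chance of m cases:

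| Shift | p = 2% | p = 5% | p = 10% |
|---|---|---|---|
| 1 SD on both | 5.1% | 5.3% | 5.7% |
| 2 SD on one, 1 SD on the other | 5.4% | 6.1% | 7.3% |
| 2 SD on both | 6.4% | 8.7% | 12.8% |
| 3 SD on both | 9.8% | 17.0% | 28.6% |

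One case shifted on one measure only gives 5.0% to 5.1%, so no inflation.

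**4. Choosing after the results, with no shift.** Reporting whichever of kept or dropped is significant gives 6.5% with one flagged participant and 7.4% with two. Weighted over p = 2 / 5 / 10%, that is 5.3 / 5.7 / 6.3%, a rise of 0.3 to 1.3 percentage points.

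**5. Effect on Aim 1.** One case shifted by 1 SD moves its group mean by 1/10 = 0.1 SD. The standard error of an unadjusted 10-versus-10 difference is √(1/10 + 1/10) = 0.447 SD, so the shift is 0.1/0.447 = 0.22 standard errors.

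**6. For scale.** Section 3.2.6 names three cognitive domains and section 3.3 refers to MRI metrics in the plural. If tests were independent, three at 5% give 1 − 0.95^3 = 14% and six give 1 − 0.95^6 = 26%. The rise in step 4 is small beside that.

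**7. What a with/without display would bring.** Leaving out one or two obese participants raises the critical |r| from 0.632 to 0.666 or 0.707. At a true r of 0.7, power falls from 68% to 62% or 55%, and the two versions disagree on significance in about 11% or 19% of samples by chance alone.

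**The case for a change.** The strongest case for a change is that an exclusion defines who belongs but not what happens to scans and scores already collected. The investigators' check on arrival names no laboratory result. The insulin-resistance covariate serves Aim 1 only. A few sentences, written before the data are examined, would close the matter with no added test or participant, and pilot status does not explain a blood test with no purpose.

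Much of this stands as description. No section links OGTT or HbA1c results to the criterion, section 3.2.5 is silent on timing and use, and the schema and section 3.1.1 word the diabetes exclusion differently. What does not follow is a need to amend. The population is settled, so the open question is one of display. The larger error rates depend on assumed prevalences and on shifts of 2 to 3 SD on both measures. Even then, the term false positive is debatable: if diabetes moves both measures, the association in the sample is real but confounded. A second set of results on eight or nine people could be read only descriptively.

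**Conclusion.** No change to the plan is called for. The silence on HbA1c and the uneven wording of the exclusion are clerical, and a reader can resolve the wording from the schema and the first sentence of section 3.1.1. How to present a participant with a diabetic-range result is a reporting matter that analysts handle as routine.

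For moderate assumptions (2% to 10% undiagnosed, 1 SD on both measures) the Aim 2 error rate is at most 5.7% against 5%. One case moves the Aim 1 contrast by 0.22 standard errors per SD of shift. The conclusion would weaken only if undiagnosed diabetes were common among those enrolled and moved both the MRI metric and cognition by 2 SD or more. The documents give no reason to expect this, and they present a funding-sized pilot rather than a confirmatory test. A line in section 3.2.5 on the timing and purpose of HbA1c would be tidy, but no planned analysis depends on it.

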3.2.3.2 MRI

MRI-based scans will be performed in the Siemens 3T Prisma in the Center for Clinical Imaging Research (CCIR) at Barnes-Jewish Hospital or in the East Building at WUSM. Scans will be performed over 1.5 hr.

High-resolution structural images will be acquired using a sagittal MP-RAGE 3D T1-weighted sequence (sagittal orientation, TR=2500 ms, TE=2.9 ms, TI=1070 ms, voxel res=1x1x1mm, frames=176, Flip=8, Time=6:09-8:42 min.) and T2-weighted anatomical images (sagittal orientation, TR=3200 ms, TE=564 ms, voxel res=1x1x1mm, frames=176, Flip=120, Time=4:42-6:51 min). These structural images will be used for between-subject registration and anatomic localization.

We will acquire a DWI sequence optimized for DBSI analyses with 2 echo planar sequences with a multiband factor of 3 and 102 volumes each, one with b-values ranging from 0-1500 and the other 0-3000 s/mm² (transverse orientation, TR=3500 ms, TE=83 ms, voxel res=2x2x2 mm, Time=6:14 min).

Three 6 min blood oxygenation level dependent (BOLD) functional MRI (fMRI) scans will be acquired for analyses of functional connectivity of networks at rest. Sequence parameters: 64 slices; transverse orientation; TR=1230 ms; TE=33 ms; FA=63 degrees; FOV=216 x 216; voxel resolution=2.4 x 2.4 x 2.4 mm.

Gradient Echo Plural Contrast Imaging (GEPCI)/SMART. Used to quantify tissue alterations that reflect integrity of cellular brain structure. (1) GEPCI: TR=50 ms, 10 echo times equally spaced from 4-40ms, voxel res=1x1x2mm, FA=30 deg, Time=6:05 min. (2) SMART: TR=20 ms, TE 1,2,3=3,7,11 ms, voxel res=1x1x2mm, Time=2:01 min x 5 variations of flip angle (5, 10, 20, 40, 60 deg). This novel technique, which includes the more advanced GEPCI-based sequences qGRE and SMART, should provide quantitative *in vivo* high-resolution 3D measurements of several brain-tissue-specific relaxation properties (GEPCI metrics) of the gradient recalled echo (GRE) MRI signal. Since GEPCI metrics depend on the molecular constituents present in the brain, the GEPCI metrics can serve as surrogate markers of tissue alterations that reflect the integrity of brain cellular structure and disease-related tissue damage. These techniques are based on a standard Siemens GRE-based sequence and do not require contrast.

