3.2.4 Oral Glucose Tolerance Test (OGTT)

For the OGTT patients will be admitted to the CTRU in the a.m. after at least 8 hours of fasting. An IV will be put in place for blood draws. Patient will be asked to drink 75 grams of glucola after drawing time 0' sample of OGTT. Samples for blood glucose levels by glucose oxidase method and insulin levels and C-peptide by immulite will be measured at -5, 0, 10, 20, 30, 60 and 120 min. Insulin secretion and sensitivity will be calculated from the OGTT glucose, insulin and C-peptide levels using the homeostasis model assessment (HOMA), quantitative insulin sensitivity check index (QUICKI) and modeling of insulin secretion. Blood samples will be saved and sent to the Core Lab for Clinical Studies for measuring of peripheral immune function.

Protocol

Version 6: August 25, 2020

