3.2.7. Study Visit

3.2.7.1 Anticipated duration of entire research activity per patient

Participant involvement will last for approximately 6 hours over the span of 1-3 days including phone screening and electronic survey completion. If there is a technical problem with the MR data collection, participants may be asked to repeat the MR session. In this case, total participation would last up to 8 hours. Participants will be provided with lunch after the OGTT.

3.3. Statistical Analysis:

Aim 1: To determine if obesity is associated with increased cellularity and glial levels in the brain using MR-based Diffusion Basis Spectrum Imaging (DBSI) and qGRE (GEPCI/SMART). We will use analyses of covariance (ANCOVA) to compare MRI-based metrics between obese and non-obese controlling for age, sex, gender, and insulin resistance .
Aim 2: To determine if indicators of neuroinflammation, including cellularity and glial levels are associated with cognitive performance in obesity. We will use Pearson's *r* correlational analyses to determine whether MRI metrics relate to impaired cognition in obesity.

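### MRI may be done at either of two locations, with no rule on who is scanned where and no scanner term in the Aim 1 ANCOVA: a possible bias, not a demonstrated one, with a low-cost safeguard

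*Combined protocol and SAP*

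**What the plan says.** Section 3.2.1 states that "The MRIs will take place in a Siemens 3T scanner" at one of two named locations. Section 3.2.3.2 repeats the choice and names the model: "Siemens 3T Prisma in the Center for Clinical Imaging Research (CCIR) at Barnes-Jewish Hospital or in the East Building at WUSM". Neither section assigns participants to a location, asks for one scanner throughout, or balances the groups across locations. No section describes cross-scanner calibration. Section 3.2.7.1 allows a repeat MR session after a technical problem and does not say where it is done.

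For Aim 1, section 3.3 uses ANCOVA to "compare MRI-based metrics between obese and non-obese controlling for age, sex, gender, and insulin resistance". Scanner is not on that list. Aim 2 uses Pearson "correlational analyses to determine whether MRI metrics relate to impaired cognition in obesity".

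Section 3.1.1 sets 10 obese and 10 non-obese adults, with the number fixed by funding, and adds: "This is a pilot and feasibility study".

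**The concern.** The Aim 1 outcomes are themselves quantitative MRI metrics (DBSI, qGRE/GEPCI/SMART), so any systematic difference between scanners would enter the outcome directly. The groups are defined by BMI and are not randomised, so nothing in the design protects balance of location between them. With 10 per group, a few bookings can create a noticeable imbalance. If location differed by group, an unadjusted scanner shift would appear as part of the obesity effect. In the extreme case, with all obese participants on one scanner and all non-obese on the other, no analysis could separate the two. Location is fixed once a participant has been scanned, so balance has to be planned in advance.

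**Working it through.** **Plan's own figure.** There is none to reproduce. N = 20 rests on funding; no alpha, power, effect size or SD is given.

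**Inputs from the documents.** 10 v 10; covariates age, sex, gender and insulin resistance; two permitted locations.

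**Assumptions, not in the documents.** Two-sided alpha 5%; unit residual SD; an additive scanner offset of 0.25, 0.5 or 1.0 SD; sex and gender fitted as one term; correlation of insulin resistance with group of 0, 0.5 or 0.7. Residual df = 20 − 5 = 15 without a scanner term and 14 with one.

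**Step 1: bias without a scanner term.** Bias = (share of obese on scanner A − share of non-obese on scanner A) × offset.

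- 7 v 3: (0.7 − 0.3) × 0.25 / 0.5 / 1.0 = 0.10 / 0.20 / 0.40 SD.
- 8 v 2: (0.8 − 0.2) × 0.25 / 0.5 / 1.0 = 0.15 / 0.30 / 0.60 SD.

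In simulation these values did not change with the correlation between insulin resistance and group.

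**Step 2: type I error without a scanner term.** Simulated with no true group difference, 200,000 replicates per case, offsets 0.25 / 0.5 / 1.0 SD:

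| Correlation of insulin resistance with group | 7 v 3 | 8 v 2 |
|---|---|---|
| 0 | 5.3 / 6.2 / 8.6% | 5.9 / 8.3 / 17.1% |
| 0.5 | 5.3 / 5.9 / 7.9% | 5.8 / 7.5 / 14.0% |
| 0.7 | 5.0 / 5.5 / 7.0% | 5.4 / 6.8 / 11.1% |

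With a scanner indicator in the model (offsets 0.5 and 1.0 SD), bias is 0 and type I error 4.9–5.1% at 5 v 5, 7 v 3 and 8 v 2. The zero follows from simulating a purely additive shift.

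**Step 3: how likely such splits are by chance.** If each person's location were a coin toss, the counts on scanner A in the two groups are independent Binomial(10, 0.5). The gap between them reaches 4 or more (7 v 3 or worse) with probability 11.5%, and 6 or more (8 v 2 or worse) with probability 1.2%. Averaged over coin-toss bookings, type I error is 4.9–5.1%. What remains is noise: residual variance is multiplied by 1 + 0.25 × offset². For 0.5 and 1.0 SD the residual SD therefore rises by √1.0625 = 1.03 and √1.25 = 1.12, that is, by 3% and 12%.

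**Step 4: cost of the scanner term.** The group difference has SE = √(0.2 × VIF), and the detectable difference comes from the noncentral t at 80% power. With VIF = 1 and 15 df it is 1.34 SD. That ignores chance correlation of group with age, sex and insulin resistance at n = 20. Drawing those covariates at random gives a mean VIF of about 1.22, and 1.34 × √1.22 = 1.48 SD. On that basis:

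| Correlation of insulin resistance with group | No scanner term | Balanced scanner term |
|---|---|---|
| 0 | about 1.48 SD | about 1.49 SD |
| 0.5 | about 1.73 SD | about 1.77 SD |
| 0.7 | about 2.13 SD | about 2.20 SD |

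With the term but without balance, at correlation 0, it is about 1.62 SD at 7 v 3 and 1.86 SD at 8 v 2. Lost balance therefore costs far more than the degree of freedom.

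**The case against.** Every harm above needs two things the documents do not supply: an offset between scanners, and a link between location and group. Several passages lean the other way. Section 3.2.3.2 names one model and gives one set of acquisition parameters, not one per location. The diffusion, GEPCI and SMART sequences behind the Aim 1 metrics each have a single stated time. One weight limit, ">350 lb (scanner weight limit"), applies to everyone, and one visit pathway is described: "The OGTT, 90 min MRI scan and cognitive testing will occur during one on-site study visit day". The study is a pilot, and under haphazard booking the damage at modest offsets is slight. All of this stands, and it keeps the point at the level of an optional improvement. It does not close the gap: a common model and protocol make a large offset harder to assume but do not exclude one, and nothing commits the study to haphazard or balanced booking.

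Three stronger readings are tempting and not supported:

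- **That the two locations have different scanners.** Section 3.2.1 says only Siemens 3T, while 3.2.3.2 says Prisma; a less specific description is not a contradiction. The T1 and T2 times are given as ranges, but the text does not tie the ranges to location, and those images serve registration and anatomical localisation rather than the Aim 1 outcomes.
- **That heavier participants will be sent to one location.** No passage says so.
- **That the Aim 1 test has an error rate of 17%.** That figure needs an 8 v 2 split, a full 1.0 SD offset and insulin resistance unrelated to group, all at once.

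**Conclusion.** The gap is real: two permitted locations, no assignment or balance rule, and a stated covariate list without scanner, in a non-randomised 10 v 10 comparison of MRI metrics. A reader might infer that the Aim 1 contrast is confounded by scanner; the documents do not show that. They support a possible bias of unknown size. If there are two scanners with an additive offset of 0.5 / 1.0 SD, the bias would be 0.20 / 0.40 SD at 7 v 3 and 0.30 / 0.60 SD at 8 v 2, with type I error of about 6 / 9% and 8 / 17% when insulin resistance is unrelated to group, and lower when it is related. If booking is haphazard, the main consequence is extra noise. This is worth considering because the safeguard costs little and cannot be fully applied after scanning. It is not an error in a stated figure. If sex and gender were fitted as separate terms, one further residual degree of freedom would go and the conclusion would not change.

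**What to change.** **Sections 3.2.1 and 3.2.3.2.** State whether one or two scanners will be used. One scanner for all participants is preferable where availability allows; it removes the issue without using a degree of freedom. The documents do not describe availability, so the cost of that option cannot be judged from them. If both locations are used, schedule equal numbers of obese and non-obese participants on each scanner. The two scanners need not be used equally often; the match between groups is what matters. Record the scanner for each analysed session, including repeats under 3.2.7.1.

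**Section 3.3.** If both scanners are used, add a scanner indicator to the Aim 1 ANCOVA. Leave the Aim 2 analysis as it is.

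**Cost.** One residual degree of freedom, no extra scans, and a scheduling constraint. With balance, the detectable difference rises by about 0.01 SD at correlation 0 (1.49 − 1.48), 0.04 SD at 0.5 (1.77 − 1.73) and 0.07 SD at 0.7 (2.20 − 2.13).

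**Limit.** The indicator removes an additive shift only. It does not deal with a scanner effect that differs between obese and non-obese participants; using one scanner avoids that question.
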